8.2.1 Inclusion Criteria

- 1) Histologically proven pancreatic adenocarcinoma with measurable disease, defined as at least 1 unidimensionally measurable lesion on imaging as defined by RECIST 1.1 criteria.
- 2) A known BRCA-associate genetic mutation OR family history suggesting of a breast or ovarian cancer syndrome, as defined by one or more of the following:
 - Personal or known family history of a deleterious (or indeterminate) mutation in the *BRCA1*, *BRCA2*, *PALBB2*, or one of the *FANC* genes.
 - Personal history of breast cancer and one or more of the following:
 - o Diagnosed \leq 45 years old
 - o Diagnosed at any age with ≥ 1 1st, 2nd, or 3rd degree relative with breast cancer \leq 50 years old and/or ≥ 1 st, 2nd, or 3rd relative with epithelial ovarian cancer at any age
 - o Two primary breast cancer with the first diagnosed at \leq 50 years old
 - o Diagnosed \leq 60 years old with triple negative breast cancer
 - o Diagnosed at any age with ≥ 2 1st, 2nd, or 3rd degree relatives with breast cancer at any age
 - o Diagnosed at any age with ≥ 2 1st, 2nd, or 3rd degree relatives with pancreatic cancer or aggressive prostate cancer (Gleason score ≥ 7) at any age
 - o 1st, 2nd, or 3rd degree male relative with breast cancer
 - o Ashkenazi Jewish descent
 - Personal history of epithelial ovarian cancer
 - Personal history of male breast cancer
 - Personal history of pancreatic cancer and ≥ 2 1st, 2nd, or 3rd degree relatives with breast, epithelial ovarian, pancreatic, or aggressive prostate cancer (Gleason score ≥ 7) at any age
- 3) Age ≥ 18 years
- 4) ECOG performance status 0-2 (See Table 2, Below)
- 5) Subjects with no brain metastases or a history of previously treated brain metastases who:
 - Have been treated by surgery or stereotactic radiosurgery (SRS) at least 4 weeks prior to enrollment
 - AND have a baseline MRI that shows no evidence of active intracranial disease
 - AND have not had treatment with steroids *for brain metastases* within 1 week of study enrollment
- 6) Prior therapies:
 - a. For patients stratified to the untreated arm:
 - i. Untreated patients should have received zero prior therapies for metastatic disease.
 - ii. They may have received prior adjuvant chemotherapy and/or radiation therapy, but not within 6 months prior to treatment.
 - iii. They may have received prior *palliative* radiation therapy for unresectable disease, but without any systemic chemotherapy, even as a radiosensitizer
 - b. For patients in the previously treated arm:
 - i. Previously treated patients may have received any number of prior therapies
 - ii. Patients who received prior adjuvant chemotherapy and/or radiation therapy within 6 months of treatment will be considered previously treated
 - Patients may have received any prior therapies **EXCEPT prior therapy with a PARP inhibitor**
 - iii. Timing of prior therapies:
 - At least 14 days must have passed since all prior anti-cancer therapy, including chemotherapy, biological therapy, or radiation therapy
 - However, at least 28 days must have passed since any prior antibody-based therapies (such as, but not limited to cetuximab or bevacizumab)
 - Additionally, at least 28 days must have passed since any prior investigational agent.

- All patients must have completely recovered from all transient side effects related to prior therapies
 - a. However, any side effects that are expected to be more durable or even permanent (e.g., neurotoxicity or ototoxicity) must have resolved to at least grade 1.

7) Adequate hepatic, bone marrow, and renal function:

- a. Bone Marrow: Absolute neutrophil count (ANC) $\geq 1,500/\text{mm}^3$; Platelets $\geq 75,000/\text{mm}^3$; Hemoglobin $\geq 9.5 \text{ g/dL}$
- b. Renal function: Serum creatinine $\leq 1.5 \times$ upper normal limit of institution's normal range **OR** creatinine clearance $\geq 50 \text{ mL/min}/1.73 \text{ m}^2$ for subjects with creatinine levels above institutional normal
- c. Hepatic function: AST or ALT $\leq 3 \times$ the upper normal limit of institution's normal range; bilirubin $\leq 2.5 \times$ the upper normal limit of institution's normal range.
 - i. 5FU and oxaliplatin are known to be safe to be administered in patients with such abnormal liver function tests
 - ii. ABT-888 is primarily excreted in the urine, and is not even metabolized by the liver. Thus such degree of hepatic impairment is not expected to affect the dosing of ABT-888.

8) Partial Thromboplastin Time (PTT) must be $\leq 2 \times$ upper normal limit of institution's normal range and INR (International Normalized Ratio) < 2 . Subjects on anticoagulant (such as coumadin) must have a PTT $\leq 5 \times$ upper normal limit of institution's normal range and INR (International Normalized Ratio) < 5 .

9) Subject's with significant fluid retention, including ascites or pleural effusion, may be allowed at the discretion of the PI.

10) Life expectancy > 12 weeks.

11) Women of childbearing potential must have a negative serum pregnancy test within 14 days prior to initiation of treatment and/or postmenopausal women must be amenorrheic for at least 12 months to be considered of non-childbearing potential.

12) Men and women enrolled in the protocol must agree to use adequate contraceptive measure when the female (patient, or partner of the male patient) has childbearing potential (the woman is not post-menopausal and has an intact uterus).

13) Subject is capable of understanding and complying with parameters as outlined in the protocol and able to sign and date the informed consent, approved by the Institutional Review Board (IRB), prior to the initiation of any screening or study-specific procedures.

14) Patients must have fully recovered from all effects of surgery. Patients must have had at least two weeks after minor surgery and four weeks after major surgery before starting therapy. Minor procedures requiring "Twilight" sedation such as endoscopies or mediport placement may only require a 24 hour waiting period, but this must be discussed with an investigator.

[figure not shown]

Table 2: ECOG Performance Status

8.2.2 Exclusion Criteria

- 1) CNS metastases which do not meet the criteria outlined in the inclusion criteria.
- 2) Clinically significant peripheral neuropathy at the time of randomization (defined in the NCI Common Terminology Criteria for Adverse Events Version 4.0 [CTCAE v4.0] as grade 2 or greater neurosensory or neuromotor toxicity).
- 3) Active severe infection, or known chronic infection with HIV, hepatitis B virus
 - a. Patients with chronic Hepatitis C virus *may* be enrolled if there is no clinical/laboratory evidence of cirrhosis AND the patient's liver function tests fall within the parameters set in Section 8.2.1, Inclusion Criteria number 6c, "Hepatic Function."
- 4) Cardiovascular disease problems including unstable angina, therapy for life-threatening ventricular arrhythmia, or myocardial infarction, stroke, or congestive heart failure within the last 6 months
- 5) Life-threatening visceral disease or other severe concurrent disease
- 6) Women who are pregnant or breastfeeding
- 7) Anticipated patient survival under 3 months
- 8) Regarding prior malignancies:
 - a. Patients with a second active malignancy being actively treated at the time of screening with palliative or curative intent with cytotoxic chemotherapy, surgery, or radiation are **ineligible**
 - b. Patients with **Stage III or Stage IV** cancers of any type who have completed cytotoxic chemotherapy, surgery, or radiation in the adjuvant setting within 3 years of screening are **ineligible**.
 - i. For these patients, if more than three years have passed from the completion of adjuvant therapy to screening for the current protocol, then the patient **is eligible** for enrollment.
 - c. However, patients with **Stage I or Stage II** cancers of any type, and who have **completed** cytotoxic chemotherapy, surgery, or radiation in the adjuvant setting by the time they are screening for the current protocol **are eligible** for enrollment.
 - d. Patients who are being treated with adjuvant hormonal therapies, such as anti-estrogens or anti androgens and meet criteria 8.b.1 or 8.c above, **are eligible** for enrollment provided they stop the hormonal therapy prior to starting the study medications.
 - e. Finally, patients with cervical cancer in situ, in situ carcinoma of the bladder, or non-melanoma carcinoma of the skin that have been removed, **are eligible** for enrollment at any time.

Questions regarding the inclusion of individual subjects should be directed to the Principle Investigator.

- 9) Clinically significant and uncontrolled major medical condition(s) including but not limited to:
 - a. Active uncontrolled infection
 - b. Symptomatic congestive heart failure
 - c. Unstable angina pectoris or cardiac arrhythmia
 - d. Psychiatric illness/social situation that would limit compliance with study requirements.
 - e. Any medical condition, which in the opinion of the study investigator places the subject at an unacceptably high risk for toxicities.

8.2.3 Prior and Concomitant Therapy

Any medication or vaccine (including over-the-counter or prescription medicines, vitamins and/or herbal supplements) that the subject is receiving at Screening up to the Final Visit must be recorded in source documents and the case report forms (CRFs). The reason for use, date(s) of administration (including start and end dates), and dosage information (including dose and frequency) must be recorded. Any change in concomitant therapy during the study period must be similarly recorded. Questions regarding prior or concomitant therapy should be directed to one of the investigators.

8.2.3.1 Prior Anti-cancer Therapy

For purposes of this protocol, anti-tumor treatment may be defined as, but is not limited to, anti-cancer agents (cytotoxic chemotherapy, immunotherapy, or biologic therapy), radiotherapy and investigational agents. An investigational agent is any drug or therapy not currently approved for use in humans.

8.2.3.2 Prior Surgery

Patients must have fully recovered from all effects of surgery. Patients must have had at least two weeks after minor surgery and four weeks after major surgery before starting therapy. Minor procedures requiring "Twilight" sedation such as endoscopies or mediport placement may only require a 24 hour waiting period, but this must be discussed with an investigator.

8.2.3.3 Supportive Care

Subjects should receive best supportive care and treatment of symptoms during the study as appropriate, including transfusion of blood and blood products, oxygen therapy, nutritional support, intravenous fluids, and treatment with appropriate medications (antibiotics, antiemetics, antidiarrheals, and analgesics, etc.). Medications, including steroids, which are given for supportive care, such as appetite stimulation, may be given concurrently.

8.3 Efficacy and Safety Assessments/Variables

8.3.1 Efficacy and Safety Measurements Assessed and Flow Chart

Study procedures for safety and exploratory efficacy assessments will be performed as summarized in Table 3, and a checklist of study activities through cycle 2 is detailed in Table 4.

Table 3: Study Activities

	Screening	Cycle 1 and Cycle 2, Day 1 ^{aaa}	Day 3 of Each Cycle	Day 1 of every odd numbered cycle (Beginning cycle 3)	Day 1 of every even numbered cycle (Beginning cycle 4)	After every 4 cycles	Off Study	Final Follow-up Visit	Every 3 months
Informed consent	X								
Demographics	X								
Medical history	X								
Concurrent meds	X	X		X			X	X	
β-HCG	X ^{bbb}	X ^{bbb}							
Dispense Medications		X		X	X				
Disconnect 5-FU			X						
Physical exam	X	X		X			X	X	
Vital signs	X	X	X	X	X		X	X	
Height	X								
Weight	X	X		X	X		X	X	
Performance Status	X	X		X			X	X	
CBC w/diff	X	X		X	X		X	X	
Serum chemistry ^{ccc}	X	X		X	X		X	X	
PT/PTT/INR	X								
Adverse event evaluation	X	X		X			X	X	
Neuropathy QOL Assessment	X			X					
PK Sampling	See Table 5 for Details								
Radiologic evaluation and Tumor Measurements	X ^{ddd}					X ^{fff}	X ^{ggg}		
Tumor Biopsy	X						X		
Research Serum Sample	X					X	X		
Progression and Survival						X		X	X

^{aaa}For the phase I portion, if any patient has been escalated from one dose cohort to another (up or down) then that particular patient will be on Day 1 of the first two cycles of the new dose level as well.

^{bbb}Urine or Serum pregnancy test (women of childbearing potential) at screening and Cycle 1, Day 1 ONLY

^{ccc}Albumin, alkaline phos, total bili, bicarbonate, BUN, calcium, chloride, creatinine, glucose, potassium, total protein, AST, ALT, sodium.

^{ddd}Screening scans should have been within 4 weeks of starting treatment.

^{eee}Optional serial samples

^{fff}But not more than every 12 weeks, if there have been treatment delays

^{ggg}If not done within the previous 4 weeks

Table 4: Early Study Activities Checklist**Screening/Pre-Treatment**

Subject Assessment	_____
Eligibility Criteria	_____
Informed Consent	_____
Pregnancy Test (if appropriate)	_____
Radiology within 4 weeks	_____
Blood for research	_____
PT/PTT/INR	_____
Tumor biopsy	_____

Cycle 1, Day 1

Subject Assessment	_____
Pregnancy Test (if appropriate)	_____
5FU, oxaliplatin, and ABT-888 Dosing	_____
ABT-888 Pharmacogenomics	_____

ABT-888 PKs (0, .5, 1, 2, 4, and 6 hours) _____

Vital Signs	_____
5-Fluorouracil disconnect	_____
ABT-888 PKs (0, .5, 1, 2, 4, and 6 hours)	_____

Cycle 1, Day 3

Subject Assessment	_____
5FU, oxaliplatin, and ABT-888 Dosing	_____

Cycle 2, Day 1

Vital Signs	_____
5-Fluorouracil disconnect	_____

8.3.2 Study Procedures

Screening will occur within 14 days prior to administration of the first dose of ABT-888 on Day 1. For procedures performed at Screening and repeated, the later procedure performed prior to dosing, will serve as a baseline for clinical assessment.

For patients being considered for enrollment outside of Georgetown-Lombardi, all primary source documentation should be sent to the multi-institutional coordinator and the study PI, [name] for review and approval. Patients must be approved for accrual prior to starting study medications. Faxed records should be sent to [contact], with an email to the multi-institutional coordinator and [name] to confirm receipt of those records.

8.3.2.1 Informed Consent

Signed informed consent will be obtained from the subject or the subject's legally acceptable representative before any study-specific procedures are undertaken. A separate informed consent will be required for the Tumor Biopsy Tissue Collection.

8.3.2.2 Physical Examination

A complete physical examination, including neurologic assessment will be performed at the Screening Visit, on C1 and C2 D1, and then on Day 1 of every odd numbered cycle and at the Final Visit. Any significant physical examination findings after the administration of the first dose of ABT-888 will be recorded as adverse events. Body weight will be recorded during every physical exam. The subject will wear lightweight clothing and no shoes during weighing. Height will be measured at the Screening Visit only; the subject will not wear shoes.

8.3.2.3 Medical History

The following information will be collected during the Screening Visit:

- 1) Complete medical history, including documentation of any clinically significant medical condition
- 2) History of tobacco and alcohol use
- 3) Presence and severity of any symptoms/conditions associated with metastatic pancreatic cancer
- 4) Detailed oncology history, including:
 - a. Date of primary cancer diagnosis
 - b. Pathology (histology or cytology) of primary tumor
 - c. Metastasis information (including the location)
 - d. Surgical history
 - e. Anti-cancer and radiation treatments administered (including dates and type of modality)
- 5) At each visit, the subject's medical history will be reviewed and any changes from baseline will be recorded on the adverse event CRF. On C1D1 any changes observed from the screening assessments, prior to dosing, will be recorded in the subject's medical history. All medication (prescription or over-the-counter, including vitamins and/or herbal supplements) will be recorded beginning with the Screening Visit and continuing up through the date of the Final Visit.

8.3.2.4 Vital Signs

Vital sign determinations of heart rate, blood pressure and body temperature will be obtained at the Screening Visit, on C1 D1, C1 D3, and on Day 1 and 3 of subsequent cycles and at the Final Visit. If possible, blood pressure and heart rate measurements should not immediately follow scheduled blood collections.

Please note: patients do not need to return to the study institution for 5FU pump disconnect. The disconnect can be provided at their primary (local) oncologist's office OR by a qualified home nursing agency. In this case, the nurse performing the disconnect must document the time of disconnect, and the estimated volume of 5FU remaining (if any). A record of this documentation will be filed in the patient's study chart. The patient is responsible for returning the 5FU pump.

8.3.2.5 Pregnancy Test

For female subjects of childbearing potential, a serum pregnancy test will be performed at the Screening Visit within 14 days of C1D1 and a urine pregnancy test will be done at the C1D1 visit prior to the first dose of study drug. Subjects considered not of childbearing potential must be documented as being surgically sterile or post-menopausal (for at least 1 year). The test results must be reviewed and determined to be negative prior to dosing. If the urine pregnancy test is positive at C1D1, it should be confirmed by a serum pregnancy test. The

test may be repeated at the discretion of the investigator at any time during the study. Should a female study subject become pregnant or suspect she is pregnant while participating in this study, she should inform the treating Investigator immediately.

8.3.2.6 Clinical Laboratory Tests

All subjects will undergo the laboratory assessments outlined in Table 3.

- 1) Hematology and chemistry samples will be collected at the Screening Visit, and on Day 1 of each cycle and at the Final Visit. For Day 1 of each cycle after Cycle 2, hematology and chemistry samples may be collected up to 48 hours prior to the scheduled visit.
- 2) PT/INR and PTT will be collected at Screening.

Laboratory samples for this study will be assessed using the certified laboratories at investigators' institutions, or at a clinical laboratory such as Quest or LabCorp. The PI or sub-investigator will review, initial and date all laboratory results. Any laboratory value outside the reference range that is considered clinically significant by the investigator will be followed as appropriate. Clinically significant laboratory values will be recorded as adverse events if they meet the criteria as specified in Section 9.

8.3.2.7 Pharmacokinetic and Pharmacogenomic Analysis of ABT-888

Pharmacokinetic assessment of ABT-888 in patient plasma for the patients in the Phase I portion of the study will be performed and compared to historical controls, to identify any effect on ABT-888 PKs by oxaliplatin or 5-fluorouracil. Pharmacogenomic analyses of the variation of enzymes involved in the metabolism of ABT-888 will be performed for all patients in the study.

Of note, the Phase I portion of the study will be performed only at Georgetown University. Thus, there is no plan for PK samples to be shipped from institutions outside of Georgetown University.

8.3.2.7.1 Collection of Samples for Analysis

For pharmacogenomic analysis, on C1, D1, 3 mL of blood will be collected by any standard phlebotomy technique from a venous access point into one 3 mL potassium EDTA (purple cap) tube, and processed as below. For the PK analysis, approximately 3 mL of blood will be collected by any standard phlebotomy technique from a venous access point into one 3 mL potassium EDTA (purple cap) tube for ABT-888 concentrations on C1D1, C1D3, and C1D7 at the following times relative to the morning dose: 0 (predose), 0.5, 1, 2, 4 and 6 hours (See Table 5).

Table 5: Pharmacokinetic Sampling Schedule

	Hours after Dose of ABT-888
Day 1	0 (predose), 0.5, 1, 2, 4 and 6
Day 3	0 (predose), 0.5, 1, 2, 4 and 6
Day 7	0 (predose), 0.5, 1, 2, 4 and 6

8.3.2.7.2 Processing of Blood Samples for ABT-888 Pharmacokinetic and Pharmacogenomic Analyses

Samples will be collected via venipuncture (if an indwelling catheter must be used, 3 catheter volumes of blood must be collected and discarded prior to collection of the sample) into evacuated potassium EDTA-containing collection tubes. Sufficient blood (approximately 3mL each) will be collected to produce approximately 1.5 mL of plasma for each sample. Immediately after collection, the tubes will be inverted 8 to 10 times to ensure good mixing of blood and anticoagulant and placed in an ice bath. The drug lot number, protocol number, the subject number, the study period and/or study day, and the planned time of sampling relative to dosing and date and time of collection for each sample will be recorded. The complete process of centrifugation, transfer to polypropylene tubes and freezing should be accomplished within 60 minutes from blood draw. The processing of PK samples should be performed as described below:

1. Immediately invert the collection tubes 8 to 10 times.
2. Centrifuge sample at 1100 to 1300 \times g for 10 minutes at 2° to 8°C to separate the plasma.
3. Transfer plasma using plastic pipettes into screw-capped polypropylene tubes labeled with the protocol number, the patient number, date and time of collection relative to dosing.
4. Store samples at -20°C or colder until shipped.
5. Samples may be batched and shipped monthly.

8.3.2.7.4 Measurement Methods

Plasma concentrations of ABT-888 will be determined under the supervision of the Drug Analysis Department at Abbott. Additionally, ABT-888 metabolite(s) concentrations in plasma samples may be determined.

8.3.2.8 Neuropathy Quality of Life Assessment

Patients will fill out a brief neuropathy quality of life assessment, included in Appendix 1. The assessment will be completed by the patient prior to starting therapy, and after initiating every odd numbered cycle of treatment (starting with Cycle 3).

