5.5.2 Oxaliplatin

Oxaliplatin is a potent, third generation platinum analog, that, similar to other alkylating agents, binds to DNA, forming intra-strand cross links and DNA adducts. These DNA abnormalities inhibit DNA replication and transcription. Oxaliplatin can be administered as a single agent, but is typically given in combination with 5FU (see FOLFOX, below). It can be safely administered in patients with hepatic or renal dysfunction. The primary side effects include neurotoxicity (cold hypersensitivity and paresthesias) which can be dose limiting and also increase with repeated cycles of administration. Additionally, oxaliplatin can cause nausea, vomiting, diarrhea, and myelosuppression, all of which tend to be relatively mild. Rarely, patients may experience laryngospasm at the time of administration, which is often ameliorated by slowing the infusion and co-administration of benadryl.

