7.2 Secondary Objectives

7.2.1 Secondary Clinical Objectives To determine, in patients with metastatic pancreatic cancer treated with ABT-888 combined with 5FU and oxaliplatin:

- 1) Disease control rate (CR+PR+SD at 6 months)
- 2) Progression free survival
- 3) Overall survival
- 4) Time to disease progression
- 5) Duration of disease control
- 6) Tolerability and safety of the combination
- 7) Degree of Neuropathy, as measured by the FACT/GOG-NTX-4 (Version 4)

7.2.2 Secondary Scientific Objectives To associate the response rate of ABT-888 plus 5FU and oxaliplatin to:

- 1) Tumors that have decreased expression of or mutations in BRCA-1 or -2 or related pathway genes
- 2) PARP activity levels in serial tumor samples
- 3) Expression levels of DNA repair enzymes in tumor tissues
- 4) Pharmacokinetic and pharmacogenomic parameters associated with the metabolism of ABT-888
- 5) To isolate and propagate tumor cell lines obtained from patient samples and circulating tumor cells

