Study activities are presented in Table 3, and an early study activities checklist through cycle 2 is detailed in Table 4. Screening will occur within 14 days, prior to administration of the first dose of ABT-888 on Day 1 (baseline imaging scans must be done within 28 days of Day 1). All patients with biopsy-able tumor deposits will undergo the pre-treatment tumor biopsy prior to cycle 1, Day 1. During cycles 1 and 2, subject assessments (physical examinations including neurologic assessment, vital signs, performance status, medication review, chemistry, hematology and adverse event evaluations) will be conducted on Day 1 of each cycle. Beginning at cycle 3, patients will be seen on Day 1 of every other cycle (i.e. C3, D1; C5, D1; C7, D1, etc). Study procedures may be performed 2 days before or after the scheduled visit date, due to unforeseen or unavoidable circumstances. The neuropathy quality of Life assessment will occur during treatment for each odd-numbered treatment. Restaging studies will be performed every 4 cycles (or not more than every 12 weeks if there have been treatment delays). Patients who are adequately tolerating therapy, and whose restaging studies reveal no evidence of disease progression, by RECIST 1.1 criteria, will continue on study for an additional 4 cycles.

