8.5.1 Discontinuation of Individual Subjects

When a subject discontinuation from the study (without reaching a protocol-defined endpoint) is planned, the investigator will notify the clinical team representative via telephone as soon as possible (provided, in each case, subject care and safety are not compromised). When a subject discontinues the study, a Final Visit will be conducted (preferably prior to the initiation of another anticancer therapy). However, these procedures should not interfere with the initiation of any new treatments or therapeutic modalities that the investigator feels are necessary to treat the subject's condition. Following discontinuation of the study drug, the subject will be treated in accordance with the investigator's best clinical judgment. At the Final Visit, the reason(s) for the discontinuation from the study will be recorded and a physical examination including neurologic assessment, body weight, vital signs measurement, laboratory analyses, performance status, tumor assessment, collection of unused study drug and an assessment of adverse events will be performed as soon as possible after discontinuation from the study. All subjects will have one Follow-Up Visit approximately 30 days after the Final Visit. This Follow-Up Visit does not need to be performed for subjects who have had a Final Visit conducted \geq 30 days after discontinuation of ABT-888. If a subject is discontinued from the study with an ongoing adverse event or an unresolved clinically significant laboratory result, the site will attempt to provide follow up until a satisfactory clinical resolution of the laboratory result or adverse event is achieved. In the event that a positive result is obtained on a pregnancy test for a subject during the study, the administration of study drug to that subject must be discontinued immediately.

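### The NTX-4 neuropathy questionnaire has no end-of-treatment or follow-up assessment, so patients who stop before Cycle 3 have no post-baseline score and late oxaliplatin exposure is under-sampled

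*Combined protocol and SAP*

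**What the plan says.** Section 7.2.1 lists as its seventh secondary clinical objective "Degree of Neuropathy, as measured by the FACT/GOG-NTX-4 (Version 4").

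Three places set the schedule:

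- Section 8.3.2.8: one form before therapy begins, then one "after initiating every odd numbered cycle of treatment (starting with Cycle 3").
- Section 8.1: "The neuropathy quality of Life assessment will occur during treatment for each odd-numbered treatment". It gives no starting cycle; I read it together with the other two.
- Table 3 (8.3.1): the row "Neuropathy QOL Assessment" is marked under Screening and under Day 1 of odd-numbered cycles from Cycle 3. It is blank under Off Study, Final Follow-up Visit and the three-monthly column.

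Section 8.5.1 gives the Final Visit procedures as "a physical examination including neurologic assessment, body weight, vital signs measurement, laboratory analyses, performance status, tumor assessment, collection of unused study drug and an assessment" (the last item concerns adverse events). The NTX-4 is not among them, and none is specified for the Follow-Up Visit about 30 days later.

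Section 5.5.2 describes oxaliplatin neurotoxicity as an effect "which can be dose limiting and also increase with repeated cycles of administration". The only planned analysis, in 13.5.1.2.6, cross-tabulates neuropathy with the number of cycles.

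**The concern.** If neurotoxicity accumulates, the most informative score is the one taken at a patient's total exposure. The schedule takes no such score when all treatment stops together.

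Scheduled exits make this worse. Restaging follows every fourth cycle (8.1, 10.1), and progressive disease means withdrawal (8.5). Without treatment delays, withdrawals at scheduled restaging fall after cycles 4, 8 and 12. These are even-numbered, so the last form dates from the start of the cycle before.

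Patients who stop during or after cycle 1 or 2, for toxicity or any other reason, have only the baseline form. The stake is whether a named secondary objective can be reported at the exposure each patient actually received.

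**Working it through.** The plan states no sample size, power or precision for the NTX-4, so there is no figure of its own to reproduce. The check enumerates the schedule.

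**Inputs**

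- Forms at baseline and in cycles 3, 5, 7 and so on (8.3.2.8, Table 3).
- 14-day cycles, with one oxaliplatin dose of 85 mg/m² on Day 1 (8.1).
- Form on Day 1 of the cycle (Table 3). The documents do not settle whether it comes before or after that day's dose: Table 3 gives only the day, while 8.3.2.8 places it after the cycle has been initiated. Both readings are carried.
- The form asks about the past 7 days (Appendix 1).

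**Assumptions:** no omitted or reduced doses, and all drugs stop together after cycle L.

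**Formulas.** Let m be the largest odd number with 3 ≤ m ≤ L.

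- Post-baseline forms = (m − 1)/2, or 0 if L < 3.
- Doses reflected in the last form = m − 1 (before dosing) or m (after dosing starts).
- Doses unreflected = L − m + 1 or L − m.
- Days from last form to end of last cycle = 14 × (L − m + 1).

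| Last cycle L | Post-baseline forms | Last form in cycle | Reflected, form before dose | Reflected, form after dose starts | Days to end of last cycle |
|---|---|---|---|---|---|
| 1 | 0 | none | none | none | – |
| 2 | 0 | none | none | none | – |
| 3 | 1 | 3 | 2/3 | 3/3 | 14 |
| 4 | 1 | 3 | 2/4 (50%) | 3/4 (75%) | 28 |
| 8 | 3 | 7 | 6/8 (75%) | 7/8 (88%) | 28 |
| 12 | 5 | 11 | 10/12 (83%) | 11/12 (92%) | 28 |

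From Cycle 3 on, an exit after an odd cycle leaves 1 or 0 doses unreflected, and an exit after an even cycle leaves 2 or 1. In dose terms, exit after cycle 4 means 2 × 85 = 170, or 3 × 85 = 255, out of 4 × 85 = 340 mg/m².

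The second reading is generous. A Day 1 form with a 7-day recall looks back almost entirely on the end of the previous cycle, even if it is filled in after the infusion, so the later effect of that day's dose is still missed.

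**Oxaliplatin stopped alone.** Section 9.4.3.3.2 lets the other drugs continue. If oxaliplatin last falls in cycle k and treatment continues for at least two more cycles, one of cycles k + 1 and k + 2 is odd and at least 3, so at least one form follows the last oxaliplatin dose. With only one further cycle there is a form if k is even and none if k is odd.

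**With a Final Visit form added.** Every patient who attends has at least one post-baseline score, and no oxaliplatin dose lacks a later form.

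**The case against.** The case for leaving the schedule alone has four parts.

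1. *The patients most affected by neuropathy are still scored.* Section 9.4.3.3.2 discontinues oxaliplatin for Grade 3 or 4 neurotoxicity and allows the other drugs to continue. Section 9.4.3.3.1 expects that patients treated for a year or more will mostly have stopped oxaliplatin already because of neuropathy. Such patients keep completing forms. This stands, and it limits the gap in late exposure to patients who stop everything together or soon after oxaliplatin.

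2. *Neuropathy at exit is assessed by other means.* The Final Visit includes a neurologic and an adverse event assessment, Table 3 marks the physical exam and adverse events at Off Study and Final Follow-up, and adverse events are collected for 30 days (9.3.5). This also stands. But these are clinician assessments, and the objective names the patient-reported instrument.

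3. *The direction of bias is not shown.* A reader might infer that reported neuropathy must come out too low. Patients who stop before Cycle 3 have had at most two doses, so on the protocol's own premise their cumulative neuropathy would tend to be low, and leaving them out need not lower the summary. If scores are tabulated by the cycle in which they were taken, a missing exit form reduces coverage but does not by itself understate the score at that cycle. This stands.

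4. *The endpoint is minor.* It is one of seven secondary clinical objectives in a single-arm trial, it is descriptive, and it has no bearing on the response-rate decision rules. This is true and limits the priority. It does not outweigh a change this cheap.

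**Conclusion.** The point holds for the patient-reported endpoint. No NTX-4 is scheduled at the end of treatment or afterwards. Patients who stop before Cycle 3 have no post-baseline score. Those who reach Cycle 3 and later stop all drugs together leave zero to two oxaliplatin doses unreflected in the last form. For an exit at scheduled restaging the figure is one or two doses, depending on form timing. These counts assume full dosing on a 14-day cycle.

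Stronger readings are tempting but not supported:

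- That the last oxaliplatin doses are always missed: patients who stop only oxaliplatin can complete later forms.
- That every early discontinuation goes unscored: anyone who starts Cycle 3 has at least one scheduled post-baseline form.
- That the course after oxaliplatin is invisible: forms continue for patients still on the other drugs, and clinician assessments cover exit and follow-up.
- That the result is biased low by a known amount: the documents give no rate of stopping before Cycle 3, so neither the net direction nor the size can be computed.

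What can be said is that scores at late exposure are under-sampled. This is a modest weakness in a descriptive secondary endpoint, worth correcting because the correction is small.

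**What to change.** - In Table 3, 8.3.2.8 and 8.5.1, add the NTX-4 at the Off Study/Final Visit and at the 30-day Follow-Up Visit where that visit is held. Section 8.5.1 waives the Follow-Up Visit when the Final Visit falls at least 30 days after ABT-888 is stopped; the Final Visit form then serves.
- In 8.3.2.8, state whether the odd-cycle form is completed before or after that day's infusion, and bring 8.1 and Table 3 into line.
- In 13.5.1.2.6, tabulate the end-of-treatment score against total cycles of oxaliplatin received.

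The cost is a four-item form at visits that already take place, a change to one row of Table 3 and one added tabulation. No treatment rule or primary analysis changes. Some forms will be missing because patients die or do not attend, so the number completed should be reported beside the scores.
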